#### PERIPHERAL VASCULAR INTERVENTION

1. Peripheral vascular intervention (PVI): PVI is a catheter-based or open surgical procedure designed to improve arterial or venous blood flow or otherwise modify or revise vascular conduits. Procedures may include, but are not limited to, percutaneous transluminal balloon angioplasty, stent placement, thrombectomy, embolectomy, atherectomy, dissection repair, aneurysm exclusion, treatment of dialysis conduits, placement of various devices, intravascular thrombolysis or other pharmacotherapies, and open surgical bypass or revision.

In general, the intention to perform *percutaneous* PVI is denoted by the insertion of a guide wire into a peripheral artery or vein.

The target vessel(s) and the type of revascularization procedure (eg, surgical bypass, thrombectomy, endarterectomy, percutaneous transluminal angioplasty, stent placement, thromboembolectomy, and thrombolysis) should be specified and recorded. For the sake of simplicity, this definition applies to the extracranial carotid artery and other non-cardiac arteries and veins and excludes the intracranial vessels and lymphatics.

- 2. Procedural success: In the case of percutaneous intervention for obstructive lesions, procedural success is defined as the achievement of a satisfactory final residual diameter stenosis by angiography at the end of the procedure (and without flow limiting dissection or hemodynamically significant translesional pressure gradient). The specific parameter for final percent residual stenosis is typically between <30% and <50%; selection of the appropriate percentage may vary depending upon the specific intervention applied, the vascular territory, and anticipated or desired therapeutic response. Procedural success also implies absence of in-hospital major adverse events (AEs) (eg, death, stroke, MI, acute onset of limb ischemia, need for urgent/emergent vascular surgery, and other procedure-specific major AEs). The balloon inflation, stent placement, or other therapeutic intervention may be preceded by use of adjunctive devices (eg, percutaneous mechanical thrombectomy, directional or rotational atherectomy, laser, and chronic total occlusion crossing device), as predefined in the protocol.
- 3. Procedural status: non-elective and elective:
  - a. Non-elective: Non-elective procedures include emergent and urgent procedures. A non-elective procedure is a procedure that is performed without delay, because there is clinical consensus that the procedure should occur imminently. Non-elective procedures imply a degree of instability of the participant, urgency of the medical condition, or instability of the threatening lesion. Emergent and urgent are defined as follows:
    - Emergent: A procedure that is performed immediately because of the acute nature of the medical condition (eg, acute limb ischemia, acute aortic dissection) and the increased morbidity or mortality associated with a temporal delay in treatment; or
    - Urgent: An urgent procedure is one that is not an emergency but is required to be performed on a timely basis (≤24 hours) (eg, a participant who has been stabilized

<sup>4 We note that peripheral vascular disease includes veins, arteries, and lymphatics. However, for simplicity, this definition will focus on peripheral artery and venous interventions.

- following initial treatment of acute limb ischemia, and there is clinical consensus that a definitive procedure should occur within the next 24 hours).
- b. Elective: An elective procedure is one that is scheduled and is performed on a participant with stable disease, or in whom there is no urgency and/or increased morbidity or mortality associated with a planned procedure.
- 4. Target lesion: A target lesion is any vascular segment treated or attempted to be treated during the study procedure with the index device. The target lesion is the treated segment starting 10 mm proximal and ending 10 mm distal to the index device or therapy (stent, balloon, atherectomy catheter, or aortic stent-graft).
- 5. Target vessel: A target vessel is any vessel (eg, non-cardiac or non-intracranial) that contains the target lesion treated with the study device. The target vessel includes the target lesion as well as the entire length of native vessel upstream and downstream from the target lesion, including side branches. For the arteries of the leg, the vasculature is divided into 3 vessel "levels:" aorto-iliac, femoral-popliteal, and tibial-crural.
- 6. Non-target lesion and non-target lesion revascularization: A lesion for which revascularization is not attempted or one in which revascularization is performed using a non-study device, respectively.
- 7. Non-target vessel and non-target vessel revascularization: A vessel for which revascularization is not attempted or one in which revascularization is performed using a non-study device, respectively.
- 8. Target vessel, non-target lesion and target vessel, non-target lesion revascularization: Any lesion or revascularization of a lesion in the target vessel other than the target lesion, respectively.
- 9. Target lesion revascularization: Target lesion revascularization is any repeat intervention of the target lesion (including 10 mm proximal and 10 mm distal to the index device, as target lesion is defined above) or surgical intervention/bypass of the target vessel performed for restenosis or other complication involving the target lesion. In the assessment of target lesion revascularization, angiograms should be assessed by an angiographic core laboratory (if designated). Angiograms (and core laboratory assessment thereof) and other source documentation should be made available to the CEC for review upon request.
- 10. Target vessel revascularization: Target vessel revascularization is any repeat intervention or surgical bypass of any segment of the target vessel. In the assessment of target vessel revascularization, angiograms should be assessed by an angiographic core laboratory (if designated). Angiograms (and core laboratory assessment thereof) and other source documentation should be made available to the CEC for review upon request.
- 11. Clinically driven target lesion revascularization: Clinically driven target lesion revascularization is defined as target lesion revascularization performed due to target lesion diameter stenosis >50% AND either evidence of clinical or functional ischemia (eg, recurrent/progressive intermittent claudication, critical limb ischemia) OR recurrence of the clinical syndrome for which the initial procedure was performed. Clinically driven target lesion revascularization occurs in the absence of protocol-directed surveillance ultrasound or angiography.

- 12. Vessel patency: Vessel patency at a given time point will be determined by the absence of clinically driven target lesion revascularization and/or absence of recurrent target lesion diameter stenosis >50% by imaging (eg, invasive angiography or most commonly, duplex ultrasonography). If patency data are incorporated within the primary endpoint of a clinical study, the angiographic images or duplex ultrasonographic images should be assessed by appropriate core laboratories and made available to the CEC for review upon request.
- 13. Restenosis: Re-narrowing of the artery following the treatment of a prior stenosis, defined further as follows:
  - o Binary restenosis: A diameter stenosis of >50% at the previously treated lesion site, including the originally treated site plus the adjacent vascular segments 10 mm proximal and 10 mm distal to the site (or as otherwise defined by the Protocol, as noted above); or
  - o In-stent restenosis: A previously stented lesion that has >50% diameter stenosis.

#### STENT THROMBOSIS

#### Stent thrombosis: timing

Stent thrombosis should be reported as a cumulative value over time and at the various individual time points as specified below. Time 0 is defined as the time point after the guiding catheter has been removed and the participant has left the cardiac catheterization laboratory. Stent thrombosis timing is described in Table A3.

**Table A3. Stent Thrombosis: Timing** 

Type of Stent Thrombosis	Timing
Acute stent thrombosis 	0 to 24 hours post stent implantation
Subacute stent thrombosis 	>24 hours to 30 days post stent implantation
Late stent thrombosis 	>30 days to 1 year post stent implantation
Very late stent thrombosis 	>1 year post stent implantation

- 1. Acute or subacute stent thrombosis can also be replaced by the term early stent thrombosis. Early stent thrombosis (0 to 30 days) will be used herein.
- 2. Includes "primary" as well as "secondary" late stent thrombosis; "secondary" late stent thrombosis is a stent thrombosis after a target lesion revascularization.

#### Stent thrombosis: categories

We propose 3 categories of evidence to define stent thrombosis, as follows:

1. Definite stent thrombosis is defined as follows:

Definite stent thrombosis is considered to have occurred by *either* angiographic or pathological confirmation:

- a. Angiographic confirmation of stent thrombosis is defined as:
  - The presence of a thrombus that originates in the stent or in the segment 5 mm proximal or distal to the stent and presence of at least 1 of the following criteria within a 48-hour time window:
    - Acute onset of ischemic symptoms at rest;
    - New ischemic ECG changes that suggest acute ischemia;
    - Typical rise and fall in cardiac biomarkers (refer to definition of spontaneous MI);
    - Nonocclusive thrombus; or

Note: Intracoronary thrombus is defined as a (spherical, ovoid, or irregular) noncalcified filling defect or lucency surrounded by contrast material (on 3 sides or within a coronary stenosis) seen in multiple projections, or persistence of contrast material within the lumen, or a visible embolization of intraluminal material downstream.

<sup>5 The incidental angiographic documentation of stent occlusion in the absence of clinical signs or symptoms is not considered a confirmed stent thrombosis (silent occlusion).

<sup>6 Intracoronary thrombus.

Occlusive thrombus.

Note: TIMI 0 or TIMI 1 intrastent or proximal to a stent up to the most adjacent proximal side branch or main branch (if originates from the side branch).

- b. Pathological confirmation of stent thrombosis is defined as evidence of recent thrombus within the stent determined at autopsy or via examination of tissue retrieved following thrombectomy.
- 2. Probable stent thrombosis is defined as follows:

Clinical definition of probable stent thrombosis is considered to have occurred after intracoronary stenting in the following cases:

- a. Any unexplained death within the first 30 days; or
- b. Irrespective of the time after the index procedure, any MI that is related to documented acute ischemia in the territory of the implanted stent without angiographic confirmation of stent thrombosis and in the absence of any other obvious cause.
- 3. Possible stent thrombosis is defined as follows:

Clinical definition of possible stent thrombosis is considered to have occurred with any unexplained death from 30 days after intracoronary stenting until end of study follow-up.

<sup>7 For studies with an ST-elevation MI population, one may consider the exclusion of unexplained death within 30 days as evidence of probable stent thrombosis.

# APPENDIX G: UNIVERSAL DEFINITIONS OF MYOCARDIAL INJURY AND MYOCARDIAL INFARCTION: SUMMARY FROM THE FOURTH UNIVERSAL DEFINITION OF MYOCARDIAL INFARCTION (2018)

### CRITERIA FOR MYOCARDIAL INJURY

The term myocardial injury should be used when there is evidence of elevated cardiac troponin (cTn) values with at least 1 value above the 99th percentile upper reference limit (URL). The myocardial injury is considered acute if there is a rise and/or fall of cTn values.

# CRITERIA FOR ACUTE MYOCARDIAL INFARCTION (TYPES 1, 2, AND 3 MI)

The term acute myocardial infarction (MI) should be used when there is acute myocardial injury with clinical evidence of acute myocardial ischemia and with detection of a rise and/or fall of cTn values with at least 1 value above the 99th percentile URL and at least 1 of the following:

- Symptoms of myocardial ischemia;
- New ischemic electrocardiogram (ECG) changes;
- Development of pathological Q waves;
- Imaging evidence of new loss of viable myocardium or new regional wall motion abnormality in a pattern consistent with an ischemic etiology; or
- Identification of a coronary thrombus by angiography or autopsy (not for types 2 or 3 MI).

Post-mortem demonstration of acute athero-thrombosis in the artery supplying the infarcted myocardium meets criteria for type 1 MI.

Evidence of an imbalance between myocardial oxygen supply and demand unrelated to acute athero-thrombosis meets criteria for type 2 MI.

Cardiac death in participants with symptoms suggestive of myocardial ischemia and presumed new ischemic ECG changes before cTn values become available or abnormal meets criteria for type 3 MI.

# CRITERIA FOR CORONARY PROCEDURE-RELATED MYOCARDIAL INFARCTION (TYPES 4 AND 5 MI)

Percutaneous coronary intervention (PCI)-related MI is termed type 4a MI.

Coronary artery bypass grafting (CABG)-related MI is termed type 5 MI.

Coronary procedure-related MI  $\leq$ 48 hours after the index procedure is arbitrarily defined by an elevation of cTn values >5 × for type 4a MI and >10 × for type 5 MI of the 99th percentile URL in participants with normal Baseline values. Participants with elevated pre-procedural cTn values, in whom the pre-procedural cTn levels are stable ( $\leq$ 20% variation) or falling, must meet the criteria for a >5- or >10-fold increase and manifest a change from the Baseline value of >20%, in addition to at least 1 of the following:

- New ischemic ECG changes (this criterion is related to type 4a MI only);
- Development of new pathological Q waves;
- Imaging evidence of loss of viable myocardium that is presumed to be new and in a pattern consistent with an ischemic etiology; or
- Angiographic findings consistent with a procedural flow-limiting complication such as coronary dissection, occlusion of a major epicardial artery or graft, side-branch occlusion-thrombus, disruption of collateral flow, or distal embolization.

Isolated development of new pathological Q waves meets the type 4a MI or type 5 MI criteria with either revascularization procedure if cTn values are elevated and rising but less than the pre-specified thresholds for PCI and CABG.

Other types of 4 MI include type 4b MI stent thrombosis and type 4c MI restenosis that both meet type 1 MI criteria.

Post-mortem demonstration of a procedure-related thrombus meets the type 4a MI criteria or type 4b MI criteria if associated with a stent.

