## 7.2 CV Event Endpoint Definitions

CV death, stroke, TIA, non-elective coronary revascularization, hospitalization for unstable angina, and hospitalization for HF will be defined based on the 2017 Cardiovascular and Stroke Endpoint Definitions for Clinical Trials described in Appendix F. MI will be defined based on the Fourth Universal Definition of Myocardial Infarction described in Appendix G.

An independent CEC will adjudicate all events of death and all potential or suspected CV events. Additional details will be provided in the CEC Charter.

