- The time from Randomization until the first confirmed occurrence of a composite of CHD death, non-fatal MI, non-fatal stroke, hospitalization of unstable angina, MALE, or non-elective coronary revascularization;
- The time from Randomization until the first confirmed occurrence of a composite of CHD death, non-fatal MI, non-fatal stroke, hospitalization of unstable angina, MALE, or coronary revascularization;
- The time from Randomization until the first confirmed occurrence of a composite of CV death, non-fatal MI, non-fatal stroke, hospitalization of unstable angina, MALE, other atherosclerotic events (AAA, TIA, carotid revascularization), or non-elective coronary revascularization;
- The time from Randomization until the first confirmed occurrence of a composite of CV death, non-fatal MI, non-fatal stroke, hospitalization of unstable angina, MALE, other atherosclerotic events (AAA, TIA, carotid revascularization), or coronary revascularization;
- The time from Randomization until the first confirmed occurrence of a composite of CHD death, non-fatal MI, non-fatal stroke, hospitalization of unstable angina, MALE, other atherosclerotic events (AAA, TIA, carotid revascularization), or non-elective coronary revascularization;

- The time from Randomization until the first confirmed occurrence of a composite of CHD death, non-fatal MI, non-fatal stroke, hospitalization of unstable angina, MALE, other atherosclerotic events (AAA, TIA, carotid revascularization), or coronary revascularization;
- The time from Randomization until the first confirmed occurrence of a composite of CV death, non-fatal MI, or non-fatal stroke;
- The time from Randomization until the first confirmed occurrence of a composite of CHD death, non-fatal MI, or non-fatal stroke;
- The time from Randomization until the confirmed occurrence of CV death;
- The time from Randomization until the confirmed occurrence of non-fatal MI;
- The time from Randomization until the confirmed occurrence of non-fatal stroke;
- The time from Randomization until the confirmed occurrence of non-elective coronary revascularization ;
- The time from Randomization until the confirmed occurrence of all cause death;
- The number of total events: CV death, non-fatal MI, non-fatal stroke;
- The number of total events: CHD death, non-fatal MI, non-fatal stroke;
- The number of total events: CV death, non-fatal MI, non-fatal stroke, or non-elective coronary revascularization;

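### Appendix G attaches the ischemia-evidence requirement for procedure-related MI only to raised pre-procedural troponin, which conflicts with Section 7.2.2 (minor; exploratory endpoints only)

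*Protocol*

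**What the plan says.** Protocol Section 7.2 makes the appendix the operative definition: "MI will be defined based on the Fourth Universal Definition of Myocardial Infarction described in Appendix G".

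In Appendix G, under the criteria for types 4 and 5, MI within 48 hours of a coronary procedure "is arbitrarily defined by an elevation of cTn values", with thresholds given as "elevation of cTn values >5 × for type 4a MI and >10 × for type 5 MI" of the reference limit. The break between the two troponin groups falls here: "percentile URL in participants with normal Baseline values. Participants with elevated pre-procedural cTn values". The second sentence then requires, for stable or falling raised values, the same 5- or 10-fold criterion, and that participants "manifest a change from the Baseline value of >20%, in addition to at least 1 of the following". Four items follow: new ischemic ECG changes (type 4a only), new pathological Q waves, imaging loss of viable myocardium, and an angiographic flow-limiting complication.

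Section 7.2.2 says that acute MI needs acute myocardial injury, clinical evidence of ischemia, a troponin rise or fall above the 99th percentile, and at least one listed criterion. It names no MI type and refers to Appendix G for more detail.

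MI enters the exploratory endpoints in Protocol Section 7 and SAP 2.3.3, for example "The time from Randomization until the confirmed occurrence of non-fatal MI". An independent CEC adjudicates, with details left to a charter that is not among the documents.

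**The concern.** An endpoint definition should give one answer for one event. Take a participant with normal troponin who has an elective PCI and next day has a troponin above 5 times the limit, with no symptoms, no ECG change and a clean angiogram. Appendix G, as written, calls this a type 4a MI. Section 7.2.2, as written, does not call it an acute MI.

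The population is largely one with established atherosclerotic disease, so some coronary procedures are to be expected during the year of treatment. If such rises are counted, the MI total includes events that show only that a procedure took place. They also enter composites that were written to leave elective revascularization out.

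**Working it through.** There is no plan figure to reproduce, and no calculation decides the wording. The check is a comparison of texts, followed by a count of the endpoints that can change.

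**1. What each text requires**

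| Case | Troponin condition | Further evidence required? |
|---|---|---|
| Appendix G, types 4a/5, normal Baseline | >5x (PCI) or >10x (CABG) limit, within 48 h | None stated |
| Appendix G, types 4a/5, raised and stable or falling | >5- or >10-fold and a change >20% | At least 1 of 4 items |
| Appendix G, types 4b/4c | Type 1 criteria | Yes, through type 1 |
| Section 7.2.2, acute MI, no type named | Rise or fall above 99th percentile | Clinical ischemia and at least 1 of 5 items |

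The first row stands alone. The later statement that "Isolated development of new pathological Q waves meets the type 4a MI or type 5 MI criteria" opens an extra route for values below the thresholds. It adds no condition for values above them. No passage expressly applies the list to the first row.

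**2. Signs of a drafting slip.** One list item is marked as relevant to type 4a only. The list is therefore sorted by procedure, not by Baseline troponin, which suggests that it was meant for types 4a and 5 generally. This is an inference from the protocol's own layout. The cited definition was not available to confirm it.

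**3. Which endpoints can change (SAP 2.3.3).** There are 27 time-to-event bullets. Six do not contain MI: the unstable angina/HF/TIA endpoint, limb events alone, CV death, stroke, non-elective revascularization and all-cause death. That leaves 27 − 6 = 21:
- 8 composites count any coronary revascularization. The procedure comes before the MI and is already an event, so time to first event does not change.
- 8 composites count non-elective revascularization. They change only when the procedure was elective.
- 4 bullets are the 3-point composites (CV or CHD death, non-fatal MI, non-fatal stroke). Two of them repeat the other two, so 2 are distinct. These are exposed.
- 1 bullet is non-fatal MI alone. This is exposed.

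Check: 8 + 8 + 4 + 1 = 21. Three distinct time-to-event endpoints are exposed whatever the type of procedure. The total-event counts (18 composites plus total CV events, 19 in all) can each rise, because there a second event in the same participant counts.

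**4. Direction of the effect.** Let the risk of a true MI be p on placebo and rp on obicetrapib, and let the extra procedural events have risk q on placebo and sq on obicetrapib. The observed ratio is approximately

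(rp + sq) / (p + q),

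a weighted average of r and s. If the extra events are unrelated to treatment (s = 1), the ratio moves from r towards 1. If treatment also changes how often procedures occur, s differs from 1 and the shift is smaller or different. The documents give none of p, q or s, so the size cannot be computed.

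**The case against.** **Section 7.2.2 already asks for ischemia.** This is the best defence, and it counts against the literal reading. It does not settle the matter. Appendix G places the same wording under a heading limited to types 1, 2 and 3. If Section 7.2.2 is limited in the same way, nothing restores the requirement for types 4a and 5. If it is not, it conflicts with the appendix. Either way the text needs reconciling.

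**The committee may apply the right rule anyway.** Adjudicators could use Section 7.2.2, the cited definition or their charter, or could read the list as covering both groups. This stands. A reader might infer that the effect vanishes only if the committee disregards Appendix G, but the documents do not support that, because the charter may resolve the point.

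**Appendix G does not otherwise contradict itself.** A reader might set the procedural rule against the opening of the appendix, where "The term myocardial injury should be used when there is evidence of elevated cardiac troponin (cTn) values", or against its general criteria for acute MI. Neither contradiction holds. The injury definition does not say that injury cannot also be MI, and the general criteria are headed for types 1 to 3. The conflict is with Section 7.2.2.

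**The reach is limited.** MI appears in 21 + 19 = 40 of the 27 + 19 = 46 cardiovascular bullets, and a reader might take all 40 to be distorted. The breakdown above shows otherwise. All affected endpoints are exploratory, without multiplicity adjustment and with nominal p-values where given (Protocol 9.2.1.2; SAP 3.1.6 and 3.4.3).

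**Conclusion.** The point holds as a minor defect in an endpoint definition. As written, Appendix G lets a troponin rise above 5 times (PCI) or 10 times (CABG) the limit within 48 hours count as an MI without other evidence when Baseline troponin was normal. Section 7.2.2 points the other way. It does not concern lesser rises, or types 4b and 4c.

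The endpoints exposed are time to non-fatal MI, the two distinct 3-point composites, the non-elective-revascularization composites when the procedure was elective, and the total-event counts. The LDL-C primary and the lipid secondary endpoints are not affected.

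A reader might want a figure for the dilution of the hazard ratio. The documents cannot supply one: procedure rates, the PCI/CABG split, the share with normal troponin, the frequency of isolated rises and the true MI rate would all have to be assumed. What can be said is that MI counts would be inflated if adjudicators follow the literal text, and that the exposed ratios would move towards 1 if the extra events are unrelated to treatment. The conclusion rests on the protocol's wording alone. Whether that wording departs from the cited definition was not checked.

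**What to change.** Reconcile Section 7.2.2 with the procedure-related criteria in Appendix G. After checking the cited definition, end the second sentence of those criteria at the change of more than 20%. Then add a separate sentence saying that at least one item on the list is required in both Baseline-troponin groups. In Section 7.2.2, say which MI types its definition covers. Put the same text in the CEC Charter, and re-check any type 4a or type 5 events already adjudicated.

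The cost is a sentence or two in the protocol and charter and a small case review. The downside is slightly fewer MI events in the exploratory analyses.
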